TAU + B-FIT. Patients randomized to the TAU + B-FIT condition will receive standard TAU at TLH, a combination of individual and group CBT. In addition, the patient and CFM will participate together in three B-FIT sessions of 60 minutes duration. The sessions typically will be scheduled at weekly intervals. The B-FIT protocol is designed to be manual-guided. *Session 1* includes: (a) rationale for CFM involvement and psychoeducation about alcohol problems; (b) interventions to identify ways that the patient and CFM can be supportive to each other; (c) interventions to identify a shared positive activity for the patient and CFM; (c) introduction to effective communication, and a communication handout. *Session 2* includes: (a) brief review of the results of the supportive behaviors and shared positive activity and discussion of problems encountered; (b) selection of a second activity with implementation plans that address any problems encountered in implementing the first activity; (c) review of the communication handout; (d) therapist coaching of the patient and CFM to try out one effective communication skill and then therapist helping the patient and CFM to use better communication skills for the balance of the session; (e) introduction to the recovery contract, including identification of specific patient behavior for the CFM to reinforce (treatment attendance or medication), and what CFM behavior will be used as the reinforcer; (f) development of a written recovery contract and discussion of potential problems in implementation of the contract. *Session 3* includes: (a) review of the supportive behaviors, shared positive activity, and recovery contract; (b) review of the second communication handout; and (c) role play rehearsal to apply communication skills to discussion of a specific topic. The three sessions will follow a similar *structure*, regardless of the relationship status of the CFM and whether or not the patient and CFM live together. The *content* of the sessions will be tailored to the specific relationship. For example, an intimate other might provide a backrub to a patient as a reinforcer; a sibling might take the patient out for dinner as a reinforcer. Consistent with a behavioral approach, the therapist will help the patient and CFM develop a concrete plan for the implementation of each intervention that is tailored to their relationship and living situation. Each implementation plan will specify the day(s) and time(s) that skills will be practiced, and also identify barriers to implementation.

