
Treatment fidelity. To measure treatment fidelity to ABCT, the PI and colleagues developed the 37-item Couples Treatment Integrity Rating Scale (C-TIRS (Hallgren et al., under review). Because ABCT includes interventions not relevant to B-FIT, the C-TIRS will be shortened to eliminate CBT items; other items will be reworded to assess interventions with family member rather than just an intimate partner. Sessions will be digitally recorded and rated for fidelity by graduate students trained to use the modified C-TIRS, using training and reliability procedures used previously in our lab.

Therapist selection, training, and supervision. B-FIT therapy sessions will be provided by a TLH clinician. Clinician training will include four elements: (a) didactic material on the rationale for B-FIT and each B-FIT intervention as well as a detailed description of each intervention; (b) role play rehearsal of each intervention; (c) supervised practice with the B-FIT manual with the first six patients/CFMs in which each audio-taped session will be reviewed by [name], or [name] and feedback provided to the clinician; (d) additional didactic training and role play rehearsal with the modified B-FIT protocol after the pilot testing and second round of focus groups. Treatment delivery will be monitored throughout the small clinical trial and Drs. [name], [name], and [name] will continue to listen to session tapes and give feedback to study clinicians.

Within treatment data collection. At TLH, patients and CFMs will complete measures of patient drinking since the last session, CFM level of distress, patient and CFM use of B-FIT interventions, and satisfaction with the treatment session (see Table 1). Patients and CFMs will each be compensated \$10 for completing within-treatment forms after each session.

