Cross-level interactions will be tested via the *t*-statistic to identify potential time by group interactions in changes in alcohol use. Type I error will be adjusted to $\alpha = .05/2 = .025$ to account for the correlation between PDA and PDH.

Aim 2c. This aim will investigate whether the relative benefit of B-FIT occurred for the presumed reasons. As such, this aim will focus only on participants assigned to the B-FIT group ($n = 40$ at baseline). Tests of mediation will use a product-of-coefficients approach with a bootstrapping procedure (Hayes, 2009). This choice provides the most powerful test of mediation with smaller samples and does not assume normality in the distribution of ($a'b'$) product terms (Preacher and Hayes, 2008; Hayes, 2009). Three active ingredients of B-FIT will be investigated separately: (1) teaching skills to reinforce change, (2) teaching skills to increase positive exchanges, and (3) teaching skills to improve communication, all of which are measured within treatment by the modified C-TIRS. Baseline values of mediators will be entered into all planned analyses as covariates. Overall, we will conduct six mediational tests. First, we will conduct 3 mediational tests to evaluate our prediction that teaching skills to reinforce change will increase 4-month abstinence (PDA) by mobilizing three mediators during the treatment phase of the study (TAU treatment adherence, commitment to abstinence, and perceived family support). The fourth test will examine if teaching skills to reinforce change increases family satisfaction (month 4) through enhanced impressions of perceived family support (within treatment). Our fifth test will examine if teaching skills to enhance positive family exchanges produces increased family satisfaction (month 4) by increasing positive shared time (within treatment). Finally, we will assess if teaching skills to improve communication increases 4-month family relationship satisfaction by mobilizing more positive partner communications within treatment. No adjustment for inflated Type I error is planned for these six tests.

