Two post hoc strategies will be used to assess the confidence we can place on the results of our unprotected tests. First, we will employ a multiple mediational model (Hayes, 2009) to examine the actions of one B-FIT active ingredient, teaching skills to reinforce change. Here, if two or more of the mediators linked with this active ingredient are found to be significant in the primary analyses we will enter those mediators into a single multiple mediation model. Although this approach lacks the precision of the primary analyses, it does address the concern of potential mediator multicollinearity and the likely erroneous rejections of null hypotheses. Second, we will descriptively assess the magnitude and consistency of *a* and *b* path estimates generated in our primary mediational analyses. Using meta-analytic techniques, for example, we will determine if the *a* ($n= 5$) and *b* ($n=6$) path parameter estimate distributions are homogeneous or not using the *Q* statistic (Borenstein, Hedges, Higgins, & Rothstein, 2009). We believe that the rejection of the assumption of homogeneity will provide important descriptive information in the identification of “key signals” or actions among the active ingredients and presumed mediators.

Aim 2d. Moderators of B-FIT Response. Three classes of moderators will be collected at the intake interview and examined in these exploratory analyses: (1) demographic variables, (2) psychological variables, and (3) familial distress/support, such as perceived social support from family. Primary interest will focus on the moderating effect of these variables on monthly PDA and PDH while secondary analyses will assess the extent to which these moderators influence family relationship satisfaction. All moderators will be binary, and we will use median splits on continuous moderator variables to generate groups with equal number of patients, e.g., patient age. Two longitudinal HLM growth models will assess potential moderating effects of patient characteristics on treatment effectiveness using PDA and PDH. Baseline value of the dependent measure will be entered as a covariate and monthly PDA and PDH will be the dependent measure in the hierarchical linear model. The time effect will be restricted to the linear term and a given moderator variable will be entered in level two of the model. Additional terms entered in level 2 of these models will include a dummy coded

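### Aim 2c tests each B-FIT ingredient in its own mediation model; if ingredient scores are correlated and an omitted ingredient moves the same mediator, the effect can be credited to the wrong ingredient

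*Combined protocol and SAP*

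**What the plan says.** In the combined protocol and SAP, the Aim 2c text under Data Analysis/Statistical Considerations restricts the analysis to the B-FIT arm (40 at baseline). It names three ingredients: skills to reinforce change, skills to increase positive exchanges, and communication skills. "Three active ingredients of B-FIT will be investigated separately", "all of which are measured within treatment by the modified C-TIRS". On covariates it says only that "Baseline values of mediators will be entered into all planned analyses as covariates". It adds: "Overall, we will conduct six mediational tests", and "No adjustment for inflated Type I error is planned for these six tests".

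The TAU + B-FIT description under Treatment Conditions sets out three 60-minute sessions. Session 1 covers supportive behaviours, a shared activity and "introduction to effective communication, and a communication handout". Session 2 has a second activity, communication coaching and the recovery contract. Session 3 reviews the activity and the contract and rehearses communication. Under Treatment fidelity, the sessions are recorded and "rated for fidelity by graduate students trained to use the modified C-TIRS".

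Two post hoc strategies follow the six tests. One is a multiple mediation model "to examine the actions of one B-FIT active ingredient, teaching skills to reinforce change". The other applies the Q statistic to the 5 a-path and 6 b-path estimates.

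**The concern.** How much of each ingredient a dyad receives is not randomised; it is observed variation within one arm. Zero correlation among the three scores would therefore be a special case. Clinician skill, rater tendency or dyad engagement could push the scores up together, while competition for time in a 60-minute session could push them apart.

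A model with one ingredient gives it credit for whatever correlated ingredients do to the same mediator. The design makes this hard to notice. All three tests on percentage of days abstinent use the reinforcement score alone, so if communication teaching raises perceived family support, only reinforcement can be credited. The other three tests share one outcome, month-4 family satisfaction.

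At stake is how the Aim 2c results may be worded: as a statement about a particular ingredient, or about B-FIT content generally.

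**Working it through.** **The plan's own counts.** The six tests, as ingredient → mediator → outcome:

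1. reinforcement → TAU adherence → days abstinent
2. reinforcement → commitment → days abstinent
3. reinforcement → family support → days abstinent
4. reinforcement → family support → satisfaction
5. positive exchanges → shared time → satisfaction
6. communication → partner communication → satisfaction

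Tests 3 and 4 share an a path, so there are 5 distinct a paths and 6 distinct b paths, as stated. This fits one ingredient per test. The counts alone would not rule out other ingredients as covariates, but the covariate sentence names none. Retained B-FIT sample: 40 × 0.85 = 34, as in the power paragraph.

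**Do the post hoc checks help?** The multiple mediation model holds several mediators of one ingredient. The Q statistic summarises path estimates that are already unadjusted for the other ingredients. No planned analysis holds two ingredient scores, and no correlation among the scores is planned for reporting.

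**Direction of the bias.** With standardised scores equally correlated at r, the a path in a one-ingredient model is

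a(separate) = a(tested) + r × (sum of the omitted ingredients' effects on that mediator).

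Both r and an omitted effect must be non-zero for bias. For an inert tested ingredient, one omitted path of .5 and b = .5, the expected spurious indirect effect is r × .5 × .5: .075 at r = .3, .125 at r = .5 and .175 at r = .7. Simulated means were .07, .12 and .18.

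**Frequency.** Monte Carlo with n = 34 and a 95% percentile bootstrap; the inert ingredient is tested while one other ingredient truly moves the mediator. r and all paths are assumptions. Share of trials declaring the inert ingredient mediated, one-ingredient model:

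| r | a = .5, b = .4 | a = .5, b = .5 | a = .5, b = .6 | a = b = .3 |
|---|---|---|---|---|
| 0 | 3% | 5.4% | 5% | – |
| .3 | 8% | 13.4% | 17% | – |
| .5 | 17% | 24.6% | 35% | 4.0% |
| .7 | 27% | 44.4% | 56% | 9.8% |

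The b = .4 and b = .6 columns include the baseline mediator as covariate; the other two do not. Repeat runs, some with larger residual variance, widen the a = .5 results to roughly 15–35% at r = .5 and 25–60% at r = .7. With all three scores in the model the rate was about 1–5% throughout.

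**Negative correlation (r = −.3, b = .5).** If all three ingredients act on the mediator with a = .35, the separate a path shrinks to .35 × (1 − .6) = .14. The tested ingredient is then detected in about 11% of trials separately and about 30% jointly. If only the tested ingredient acts on its mediator, the order reverses: about 40% separately and 27% jointly.

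**Cost of the joint model.** Variance inflation = 1/(1 − 2r²/(1 + r)): 1/(1 − .5/1.5) = 1.5 at r = .5, and 1/(1 − .98/1.7) = 2.4 at r = .7. Detection of a true ingredient (a = .5):

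- r = .5: from .34 to .25 (b = .4) and from .73 to .58 (b = .6), a loss of 26% and 21%.
- r = .7: from .39 to .20 (b = .4) and from .76 to .47 (b = .6), a loss of 49% and 38%.

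**The case against.** The strongest reply is that correlation alone does no harm; an omitted ingredient must also move the tested mediator. The plan pairs each ingredient with different mediators, and nothing in the documents says that communication teaching, for example, moves TAU adherence. This stands. The high rates come from assuming a cross-effect of .5, and with paths of .3 the rate stays near nominal. The pairing is itself a hypothesis, however, and the planned models cannot check it.

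A second reply is that a joint model gives up power in a small sample, while the plan chose its mediation method for power in smaller samples. Nor does adjusting for two sibling scores make ingredient dose randomised: dyad responsiveness could still drive both scores and mediators, and if the correlation is rater variance, adjustment may remove real signal. This also stands. It argues against making the joint model the sole gate, not against reporting it.

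Third, Aim 2c is described as a preliminary test of a methodology, and its tests are acknowledged to be unprotected. That lowers the stakes. But the methodology concerns active ingredients, so whether it can tell them apart bears on its purpose.

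A reader might go further and infer that the wrong component could be kept in or dropped from the manual. The documents do not support that. The trial's materials are revised after pilot and focus-group feedback and finalised in August 2016, before recruitment opens in October 2016. Aim 3 covers a manual for a larger trial but ties no component decision to Aim 2c. Nor do the documents support a general claim that competition for session time hides real effects; that requires the other ingredients to act on the same mediator.

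**Conclusion.** The point holds as a limit on what Aim 2c can conclude. As written, a significant indirect effect for one ingredient cannot be separated from effects of the ingredients taught alongside it, and no planned analysis would reveal the difference. The recovery contract begins in Session 2, so the overlap of all three ingredients is strictly in Sessions 2 and 3, with activity and communication overlapping in Session 1. Equating the contract with the reinforcement ingredient is a reading of the session content.

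The size cannot be fixed from the documents. It runs from no excess false attribution (zero correlation, or no cross-effect) to well over half of trials in the least favourable setting examined. The simulations assume equal correlations, a single cross-effect, and no direct effect of any ingredient on the outcome. They show that misattribution is possible, not that it will occur. This is an inexpensive improvement to a preliminary aim and leaves the Aim 2a comparisons untouched.

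**What to change.** Keep the six single-ingredient tests as planned and prespecify two additions:

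1. Report the correlation matrix of the three modified C-TIRS ingredient scores.
2. Repeat each test as a sensitivity analysis, with the other two ingredient scores as covariates in both the mediator and the outcome equation.

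Call a result ingredient-specific only if its estimate is similar in direction and size in the three-score model, and write down in advance what counts as similar. Otherwise report it as an effect of B-FIT content not separated by ingredient. State in either case that ingredient dose was not randomised, so both models are observational.

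The cost is SAP wording and a few more regressions on scores already collected. The sensitivity intervals will be wider, by the variance inflation and loss of detection shown above. The wording rule therefore compares estimates and does not require the joint interval to exclude zero.

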	Confidential Information Form (CASAA locator form)	Self-report	10		X	X					
	SCID-5 screener with PCL-5	Interview	10		X					X	
Pre-post patient substance use measures	Form-90	Interview	45		X						
	Form-90 follow-up	Interview	25								X
	Drinker Inventory of Consequences (DrINC)	Self-report	10		X						
	Short Inventory of Problems (SIP)		5							X	
	Inventory of Drug Use Consequences (INDUC)		10		X					X	
CFM functioning measures	Beck Depression Inventory	Self-report	8			X					X
	Beck Anxiety Inventory	Self-report	8		X						X
Biological measures	Breathalyzer	Self-report	5							X	
Mediators	Treatment Services Review (TSR: treatment attendance, use of medication, self-help group involvement)	Self-report	5					X		X	
	Commitment to Sobriety Scale	Self-report	5		X		X			X	
	Perceived Social Support – Family	Self-report	15		X					X	
	Family Environment Scale	Self-report	15		X	X				X	X
	Pleasant Events Schedule - adapted	Self-report	15		X	X	X	X	X	X	X
	FACES-IV	Self-report	5		X	X	X	X	X		
B-FIT evaluation	Helping Alliance Questionnaire	Self-report	8				X	X			
	Client Satisfaction Questionnaire	Self-report	8				X	X	X	X	
Therapist measures (all within treatment)											

Active ingredients	Clinician use of each B-FIT interventions	Self-report	5	
	Brief C-TIRS	Coders	60	
Mediators	B-FIT Session attendance	Self-report	2	
	Patient homework compliance	Self-report	2	
	CFM homework compliance	Self-report	2	
B-FIT evaluation	Helping Alliance Questionnaire	Self-report	8	
	Clinician feedback on B-FIT	Self-report	5	

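### Mediation tests 3 and 4 of Aim 2c need perceived family support measured during treatment, but Table 1 appears to schedule it only at baseline and follow-up

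*Combined protocol and SAP*

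**What the plan says.** Under STUDY DATA, II. Data Analysis/Statistical Considerations, Aim 2c is confined to the B-FIT arm (40 at baseline) and states: "Overall, we will conduct six mediational tests". Baseline values of the mediators are to be covariates.

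- Tests 1 to 3 run from teaching skills to reinforce change to month-4 percentage of days abstinent (PDA), by "mobilizing three mediators during the treatment phase of the study (TAU treatment adherence, commitment to abstinence, and perceived family support".
- Test 4 asks whether "teaching skills to reinforce change increases family satisfaction (month 4" and places the mediator in the treatment phase: "through enhanced impressions of perceived family support (within treatment".
- Test 5 asks whether teaching positive exchanges "produces increased family satisfaction (month 4) by increasing positive shared time (within treatment".
- Test 6 asks whether teaching communication skills "increases 4-month family relationship satisfaction by mobilizing more positive partner communications within treatment".

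The paragraph that follows plans a multiple-mediator model for the reinforce-change ingredient, and a *Q* test of homogeneity over 5 *a* paths and 6 *b* paths.

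Table 1 (II. Study Procedures, Mediators block) lists "Perceived Social Support – Family" as a 15-minute self-report form with two marks. The row above it, Commitment to Sobriety, has three. The Follow-up section sets the reassessment four months from baseline, about three months after the third session for dyads who complete all three.

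**The concern.** A mediation claim needs an order in time: the ingredient is delivered, the mediator moves, and the outcome follows. Aim 2c builds that order in by placing the mediators in the treatment phase and the outcomes at month 4. If family support is recorded only at baseline and follow-up, the only post-baseline score is the follow-up one.

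In test 4, mediator and outcome would then come from the same visit. In test 3, PDA is built from monthly values over the four months up to that visit, so the support score would come at or after the end of the drinking period it should explain. Abstinence could have raised perceived support as easily as the reverse. The *a* path changes too: it would describe support some three months after treatment, not support mobilised by treatment.

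The plan calls Aim 2c central to its model, and the aim exists to develop a way of studying mechanisms before a larger trial. When each mediator is measured is part of what is being developed.

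**Working it through.** No power or sample-size formula applies. The check is an enumeration of the tests and a reading of Table 1.

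**Step 1. Code the six tests (Aim 2c).**

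| Test | Ingredient | Mediator, needed within treatment | Outcome, month 4 |
|---|---|---|---|
| 1 | Reinforce change | TAU adherence | PDA |
| 2 | Reinforce change | Commitment | PDA |
| 3 | Reinforce change | Perceived family support | PDA |
| 4 | Reinforce change | Perceived family support | Family satisfaction |
| 5 | Positive exchanges | Positive shared time | Family satisfaction |
| 6 | Communication | Partner communication | Family satisfaction |

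**Step 2. Reproduce the plan's path counts.** Tests 3 and 4 share one ingredient-to-mediator path, so the distinct *a* paths number 6 − 1 = 5. Each test has its own *b* path, giving 6. Both match the plan, so the coding is the intended one.

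**Step 3. Read Table 1.** Each row has eight timing cells. Some columns are shifted in the machine-read text, so the cells are interpreted from rows whose timing is clear.

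| Row | Marked cells | What it shows |
|---|---|---|
| Inventory of Drug Use Consequences | 2, 7 | Listed as a pre-post measure |
| Short Inventory of Problems | 7 | Pre-post block, follow-up only |
| Helping Alliance Questionnaire | 4, 5 | Alliance exists only once treatment has begun |
| Family Environment Scale | 2, 3, 7, 8 | Baseline and follow-up, patient and CFM |
| Commitment to Sobriety | 2, 4, 7 | Baseline, within treatment, follow-up |
| Perceived Social Support, Family | 2, 7 | Baseline and follow-up |

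The support row has the same pattern as the pre-post drug-consequences row. It lacks the middle mark that the commitment row carries. The difference is a missing mark, and a column shift alone would not produce that.

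**Step 4. Compare with the text.** The list under Within treatment data collection covers drinking, CFM distress, use of B-FIT interventions and session satisfaction. Family support is not there. That agrees with Step 3 but does not decide it, because the list also omits commitment, Pleasant Events and FACES-IV, all of which have within-treatment marks in Table 1.

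**Step 5. Count the effect.** Tests whose mediator is family support: {3, 4}, or 2 of 6. Removing them leaves tests 1, 2, 5 and 6, so *a* = 5 − 1 = 4 and *b* = 6 − 2 = 4. The multiple-mediator model for reinforce change would have 3 − 1 = 2 candidate mediators.

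**The case against.** The strongest reply is that Table 1 is too damaged to bear the argument. Pleasant Events has seven marks, although three occasions for two respondents (3 × 2) allow six. FACES-IV has five. The two Beck inventories, both CFM measures, have their baseline marks in different cells. This stands as a caution: mark counts are not beyond doubt in this table, and the two-mark reading is well supported but not proven. It is a reason to check the original table. It does not remove the conflict between Aim 2c and the row as it reads.

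The second reply is that these are openly exploratory tests with no Type I error adjustment, and that the Aim 2a efficacy results are untouched. That is true and limits the weight of the point. It does not make a follow-up score a treatment-phase mediator.

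The third concerns the remedy. The version is dated February 12, 2017, and recruitment was planned from October 2016, so an added form cannot recover dyads already treated. The enrolment section expects about 20% of dyads not to finish three sessions. Applied to 40 B-FIT patients, that is 0.20 × 40 = 8, so a form given only at session 3 would miss about 8. Both points stand and shape the fix.

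A reader might go further and infer that tests 4 to 6 also fail because family satisfaction is not scheduled at month 4, which would make 4 of 6 tests impossible. The documents do not support that. They show only that no instrument is named for this outcome. The Family Environment Scale is marked at follow-up for patient and CFM, and the mediators of tests 5 and 6 have plausible rows with within-treatment marks (Pleasant Events, FACES-IV). The mechanism figure and the assessments appendix are not in the available text and may identify the measure. Nor do the documents show that the scale would be chosen after the data are seen.

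**Conclusion.** As Table 1 reads, tests 3 and 4, 2 of the 6 planned, have no within-treatment measurement of their mediator and cannot be carried out with the time order that Aim 2c specifies. Without them the path counts become *a* = 4 and *b* = 4, against the stated 5 and 6. This rests on one assumption: that the support row truly has no within-treatment mark in the original table. If it has one, the point falls away.

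For tests 4 to 6 the finding is smaller: "increases family satisfaction (month 4" is an outcome with no named instrument. That is a missing detail, not a demonstrated scheduling gap, and it does not add to the count of two.

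The point should be settled before the mediation analyses are run. It does not bear on the Aim 2a efficacy comparisons.

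**What to change.** 1. Check the Perceived Social Support, Family row against the original Table 1. If a within-treatment mark exists, correct the copy and stop there.
2. If it does not, add the form to the within-treatment set for the remaining B-FIT dyads. Give it at a session that non-completers also reach, or use the form from each dyad's last attended session. The last attended session is not known in advance, so the second choice means giving the form at more than one session. Timing matters as well: the recovery contract is introduced in session 2, so a form completed after session 1 would precede that part of the reinforce-change teaching. Report how many dyads have the measure.
3. If the form cannot be added, or too few dyads remain, restate tests 3 and 4 as concurrent associations and not mediation, and change the path counts to *a* = 4, *b* = 4.
4. Name, before analysis, the instrument and score meant by family satisfaction in tests 4 to 6. The choice is the sponsor's. Family Environment Scale Cohesion is available at month 4, but Aim 2a assigns it to family functioning, so adopting it would alter the hypothesis.

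Cost: option 2 adds 15 minutes of form time per administration and leaves incomplete data for dyads already treated. The patient forms that appear to be marked within treatment total 5 + 5 + 15 + 5 + 8 + 8 = 46 minutes if all are given at one session, so this would make 61. The documents do not say whether they are all given together. The $10 payment at about $20 an hour implies roughly 30 minutes. Items 3 and 4 cost wording only and can be done before the analysis planned from December 2017.
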